6.4.3.3. Tertiary Outcomes

We will use Generalized Linear Mixed Model to analyze the effect of ALTA on differences in relationship commitment (primary outcome) and patient-provider trust (secondary outcome). A Poisson regression model will be used specifying a fixed effect for time, a fixed effect for treatment, a time by treatment interaction, and a control group indicator. Only patients that declined participation in ALTA for the entire evaluation period will be included in the control group for the final analyses. Patients that crossover from the control group to intervention group and continue to participate in the evaluation will be counted towards the intervention group sample. Since they are asked the same questions, it does not impact the analyses. Random effects will be specified for person and clinic to account for the clustered nature of the dataset (observations within person and people within clinics). Relationship commitment will be defined as a continuous variable while patient-provider trust will be categorized as ordinal. Randomization of the stepped wedge design should obviate the need for adjustment, but in the case of imbalance in baseline covariates, these will be included as necessary in adjusted analyses. Sex will be accounted for as a covariate and examined as a potential moderator. All tests will be two-sided with $\alpha=0.05$ for comparison between the ALTA and UC phases.

Maximum likelihood estimation of mixed-effects models will be used to account for missing data; this is equivalent to an assumption of data missing at random. We will conduct sensitivity analyses assessing this assumption. We will also compare participants with and without missing values in baseline and site characteristics, as well as intervention vs control group status; if differential patterns emerge, we will consider using multiple imputation and/or inverse probability weighting to adjust for missing data. For our behavioral measures of commitment and trust derived from text analysis, we will use Python with a dedicated suite of libraries for sentiment analysis and emotion detection. The text processing libraries will be used to complete the pre-processing steps including tokenization, stemming, and lemmatization. Tokenization is the process of separating text into smaller units, i.e., words, characters, or subwords. Stemming and lemmatization will be done to reduce inflectional forms and derive the common base form [e.g., am, are, is → be]. Next, each document (clinical notes, transcripts, secure messages) will be represented as vectors using word embeddings. Distributional semantics models (e.g., continuous Bag-of-Words, Skip-gram, Global vectors) will be used to represent each word as a vector while preserving the contextual information of the word before the training phase. Resources such as lexicons (e.g., LIWC, EmoLex) will be used for feature extraction representing presence or absence of emotion words, and words associated with opening or closing rituals of a conversation. Next, multiple supervised and unsupervised algorithms (e.g., attention-based neural models, transformers architecture) will be trained on the dataset and an optimized model will be established via several rounds of experiments and rigorous evaluations. Once the best fitting model is established, it will be used to train on clinical notes data before and after ALTA implementation. Patient and providers' sentiment will be compared to establish how the relationship has changed through ALTA participation. we will use GLMM to analyze the effect of ALTA on the tertiary outcomes of patient state anxiety, SBP, DBP, and PDC. Since each individual outcome is of interest, testing will be 2-sided with a Type I error rate of 0.05 and no adjustment for multiple testing.

Analysis of Exit Interviews: Following best practices in qualitative analyses, we will use a grounded theory approach to analyze interviews with our key stakeholders, starting with a stratified sample informed by our contextual factors and proceeding until we reach theoretical saturation. Guided by our research questions, we will let the data itself drive our investigation and identification of emergent themes within the data through immersion in interview transcripts and a team-based approach to qualitative coding. After training, team members will independently review transcripts to identify initial in vivo open codes incorporating respondents' language. The team will then meet to discuss the codes and collectively develop a codebook. The codebook will be applied and iteratively refined during additional transcript reviews by the coders. We will progress to axial coding to relate categories and properties, and selective coding to derive core concepts, iteratively modifying codes throughout based on group consensus to increase validity. At each stage of analysis, we will convene meetings to discuss, define and refine emergent concepts and ensure appropriate application of codes throughout data sources. Emergent themes will be identified based on coded data and consensus forming discussions. Codes specifying elements related to our contextual factors, guided by our conceptual framework will also be

applied to transcripts; for example, we will look for themes related to modes of communication, characteristics of the patients, providers, and of the sites that may affect our outcomes. We will also triangulate across the qualitative and quantitative data using a mixed methods matrix approach to compare transcripts with data analyzed via NLP to identify both common themes and divergence across findings, providing valuable evidence of the validity of NLP-measured sentiments to assess commitment and trust. The team will use Dedoose software that allows for the integration of quantitative data with qualitative data.

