Medication adherence will be assessed via pharmacy refills obtained from prescription orders in the clinic EHR using the proportion of days covered (PDC) metric. The PDC is calculated as the total number of days covered by the medication divided by the number of days between the first fill of the medication in the study period and the end of the study period. Thus, as opposed to other pharmacy refill metrics, the PDC accounts for non-persistence with medications by tracking medications during the study period despite early discontinuation. We will count the days the patient was covered by each of their prescribed antihypertensive medications based on the prescription fill date and days of supply. If prescription fills for the same medication overlap, then we will adjust the prescription start date to be the day after the previous fill has ended. Patients will be considered adherent if they fill $\geq 80\%$ of their antihypertensive medications over the 12 months.

Tertiary Outcomes

Relationship commitment: To assess patients' *perceived commitment* to their PCP, we will utilize the self-report measure developed by Berry et al. in a sample of primary care patients. The 5-item measure asks patients to rate their degree of commitment to the relationship with their doctor on a 7-point Likert scale (*strongly disagree* to *strongly agree*). Sample items include: *The relationship with my doctor is...something I am committed to; something I care about; and important to me.* This measure will be administered to patients at baseline and 12 months.

To assess the *behavioral and affective indicators* of relationship commitment we will use NLP and analyze text of patient-provider interactions that

Part of the clinical interaction	Examples of relationship commitment behaviors and affect	Measurement strategy
Initiating the session	Patient and PCP creates a warm and friendly environment; collaboratively identify reason for visit and negotiate agenda	Sentiment analysis to identify affective behaviors (warmth, cheerfulness, and attentiveness) ¹⁰⁸

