Gathering information	PCP use of questions to explore a patient's problem and creates opportunities for patients to express concerns and ask questions; looks for potential barriers to communication (e.g., language, anxiety). Patient provides a complete medical history and information on current behaviors and condition from their perspective	Lexicon dictionaries (e.g., Linguistic Inquiry and Word Count (LIWC)) to identify interrogatives - e.g., asking questions ¹⁰⁵
Explanation and planning (shared decision-making)	PCP gives succinct, jargon-free information and checks patient understanding; actively involves patient in decision making process, and respects patient's decision Patient communicates their level of understanding and ask PCP to clarify information; adds perspective on treatment plans and agrees on what is feasible	LIWC to identify presence of assent words, absence of interaction qualities that inhibit openness, i.e. negative affect, anxiety, use of tentative words. ¹⁰⁵
Closing the session	PCP provides a summary of the discussion, verifies plan, and clarifies future expectations. Patient agrees on plan; clarifies what s/he should do between visits	To identify lexicons associated with closing rituals of speech acts with LIWC, and DAMSL. ^{108,107}

occur in the 12 months prior to ALTA, and over the 12 months ALTA phase. Data will be extracted from the EHR (e.g., clinical notes and free text) and MyChart secure messages to conduct these analyses. Table 1 provides examples of how we will examine patients' and providers' commitment to one another, and the associated measurement strategy, as they occur across different parts of the clinical interaction.

Patient-provider trust: To assess perceived patient-provider trust we will administer patient and provider measures developed by Thom et al. at the baseline and 12-month visit.

Patient: The 11-item Trust in Physician Scale (TPS) assesses a patient's interpersonal trust in their doctor. Responses are given on a 5-point Likert scale ranging from *totally disagree* to *totally agree*. Sample items include: “*I doubt that my doctor really cares about me as a person*” and “*If my doctor tells me to do something, then it must be true.*” The TPS has high internal validity ($\alpha=0.89$) and adequate test-retest reliability in a primary care sample. Prior research has found that TPS scores are associated with continuity of care, medication adherence, and satisfaction with care.

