6.4.3.2 Secondary Objectives Analyses

The effect of PF on BP Control

Our main clinical outcome is the proportion of patients with adequate BP control (<140/90 mmHg) at 12 months in the implementation vs. UC phase. BP control will be treated as a dichotomous outcome variable in this analysis; any patients with missing follow-up BP data will be assumed to have inadequate BP control. To examine the difference in BP control rates between the implementation and UC phases, we will utilize a generalized linear mixed model (GLMM) to assess the PF effect. A Poisson regression model will be used to predict BP control specifying a fixed effect for time, a fixed effect for treatment and a time by treatment interaction. Random effects will be specified for person and practice to account for the clustered nature of the dataset (observations within person and people within practices). As a sensitivity analysis, we will also assess an alternate definition of BP control (< 130/80 mmHg) indicated by the new hypertension guidelines. In exploratory analyses, will examine the intervention effect on BP reduction at 12 months, treated as a continuous variable. An additional sensitivity analysis will be conducted using GLMM to evaluate the effect of PF on BP reduction. We will test the treatment X time interactions in a random effects linear regression model to determine the time-specific differences BP reduction attributable to PF at the end of the implementation phase.

Randomization of the stepped-wedge design should obviate the need for adjustment, but in the case of imbalanced in baseline covariates; these will be included as necessary in adjusted analyses. All tests will be two-sided with $\alpha=0.05$ for comparison between the implementation and UC phases. Maximum likelihood estimation of mixed-effects models will be used to account for missing data; in the context of a mixed-effects model, this is equivalent to an assumption of data that are missing at random (MAR); we will conduct sensitivity analyses assessing this assumption. We will also compare participants with and without missing values with respect to baseline and practice characteristics. If differential patterns emerge, we will consider the use of multiple imputation and/or inverse probability weighting to adjust for missing data. Analyses will be conducted using Stata, SAS, and R.

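### The tertiary analysis assigns a Poisson model to a continuous and an ordinal outcome, and BP control gets Poisson with no robust variance: standard errors are wrong for the first two and conservative for the third

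*Combined protocol and SAP*

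**What the plan says.** Section 6.4.3.3 analyses commitment and trust with a generalized linear mixed model and names the family: "A Poisson regression model will be used specifying a fixed effect for time, a fixed effect for treatment, a time by treatment interaction". A few sentences later it describes the outcomes: "Relationship commitment will be defined as a continuous variable while patient-provider trust will be categorized as ordinal".

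Section 6.1.4 describes the instruments. For commitment: "The 5-item measure asks patients to rate their degree of commitment to the relationship with their doctor on a 7-point Likert scale". It does not say whether the items are averaged or summed. For patient trust: "The 11-item Trust in Physician Scale (TPS) assesses a patient's interpersonal trust in their doctor", answered on five points. That section also plans to dichotomize the patient and provider trust scores and form three congruence levels. Section 6.4.3.3 does not say whether those levels are the ordinal variable it means.

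For the main clinical outcome, section 6.4.3.2 says "BP control will be treated as a dichotomous outcome variable in this analysis" and then "A Poisson regression model will be used to predict BP control specifying a fixed effect for time, a fixed effect for treatment". On clustering: "Random effects will be specified for person and practice to account for the clustered nature of the dataset". Both sections rely on maximum likelihood. Neither names a robust variance, a dispersion parameter or another family for these three outcomes.

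**The concern.** A Poisson model has no free variance parameter: the variance equals the mean. For a bounded rating score there is no reason for that to hold. Multiplying a score by a constant multiplies its mean by that constant but its variance by the square, so the same questionnaires can yield different p-values depending on whether items are averaged or summed. A sound test statistic should not depend on that choice.

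For a 0/1 outcome the Poisson variance is p, while the true variance is p(1-p), so model-based intervals are too wide.

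The test of commitment, which section 6.4.3.3 treats as the lead outcome of the relationship aim, could be almost unable to reject or could reject too often. The BP control comparison could lose some precision. An analyst also cannot follow both statements in section 6.4.3.3. Unless the conflict is settled now, the choice will be made after data are available.

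**Working it through.** **The plan's own figure.** Section 6.4.2 claims at least 80% power for a 15-point difference in BP control and over 90% for 20 points, with 10 sites, 700 patients and ICC 0.01 to 0.05. It does not tie these to a usual-care rate, a number of periods or observations per period, so exact reproduction is not possible. A Hussey-Hughes calculation (five steps and six periods as in Figure 1, usual-care rate assumed 29%, binomial variance) gives the following, from ICC 0.01 to ICC 0.05:

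- 700 observations in total: 78.6% to 71.6% for 15 points, 95.2% to 91.5% for 20 points.
- Two observations per patient (1,400): 96.1% to 93.5% for 15 points, above 99% for 20 points.

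These figures describe a correctly specified analysis. The Poisson loss comes on top, and the point does not depend on them.

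**Formulas.** Let r be the Poisson model SE divided by the true SE. Ignoring clustering, r = sqrt(mean)/SD for a score. The true size of a nominal 0.05 test is 2(1 - Phi(1.96r)). A test with 80% power under a correct SE has its effect 2.80 true SEs from zero and rejects beyond 1.96r true SEs, so its power becomes Phi(2.80 - 1.96r).

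**Commitment.** Five items on 1 to 7 give an item mean of 1 to 7 or a sum of 5 to 35. Means and SDs are assumptions. Each pair of rows is one set of answers scored two ways.

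| Scoring | Mean | SD | r | True size | 80% power becomes |
|---|---|---|---|---|---|
| Item mean | 6 | 1 | sqrt(6)/1 = 2.45 | below 0.001% | 2.3% |
| Sum | 30 | 5 | sqrt(30)/5 = 1.10 | 3.2% | 74.4% |
| Item mean | 6 | 1.4 | sqrt(6)/1.4 = 1.75 | 0.06% | 26.5% |
| Sum | 30 | 7 | sqrt(30)/7 = 0.78 | 12.5% | not comparable (size inflated) |

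For means of 5 to 6 and SDs of 0.8 to 1.5, item-mean scoring gives r from 1.5 to 3.1.

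**Trust.** A three-level category coded 1 to 3, with an assumed mean of 2 and SD of 0.6 to 0.85, gives r from sqrt(2)/0.6 = 2.36 down to sqrt(2)/0.85 = 1.66.

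**BP control.** The 29% is the prior trial's usual-care rate quoted in section 6.4.2; 44% adds the 15-point difference. For the log risk ratio, per patient in each group:

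- Poisson variance: 1/0.29 + 1/0.44 = 5.72.
- Binomial variance: 0.71/0.29 + 0.56/0.44 = 3.72.
- r = sqrt(5.72/3.72) = 1.24. Power is Phi(2.80 - 1.96 × 1.24) = Phi(0.37), about 64% in place of 80%.
- Under the null at 29%, r = 1/sqrt(0.71) = 1.19, so the true size is 2.0%.
- At 5% vs 20%, r = sqrt(25/23) = 1.04. At 5% vs 51%, r = sqrt(21.96/19.96) = 1.05.

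**Simulation closer to the planned model.** A maximum-likelihood Poisson model with a person random intercept and fixed practice effects was fitted to 10 practices × 70 patients × 2 observations, 150 runs per setting:

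- BP control: r = 1.19 under the null (2.0% rejection) and 1.12 with a 15-point effect (77% rejection, against 83% using the empirical SD).
- Commitment as an item mean: r = 2.6 to 2.8, with 0% rejection under the null. With a 0.25-point effect, rejection was 0.7%, against 69% using the empirical SD.
- Commitment as a sum with SD 7: r = 0.87 and 12% rejection under the null. The Monte Carlo error is sqrt(0.12 × 0.88/150) = 2.7 points, and r = 0.87 alone would imply about 9%.

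**The case against.** The strongest reply has four parts.

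1. *The Poisson sentence may be carried over from the BP section, and any competent analyst would choose a suitable family.* Possibly, but the plan does match models to outcomes elsewhere: section 6.4.3.2 names linear regression for BP reduction, and transformation, rank or beta regression for PDC. Nothing marks the Poisson sentence as shorthand.

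2. *The person random effect absorbs misfit.* In part. It can take up variance above the mean, which is why r for the wide sum score rose from 0.78 to 0.87 in simulation. It cannot correct variance below the mean.

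3. *Log-link Poisson is a legitimate way to estimate a risk ratio for a binary outcome.* This stands. For BP control the defect is only that the variance estimator is unspecified, and the error is conservative.

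4. *These are secondary and tertiary outcomes.* Also true. Implementation fidelity, the primary outcome, is not analysed with this Poisson model.

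Three stronger readings go beyond the documents:

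- A reader might infer that the relationship tests will produce excess false positives. That needs a wide sum score (SD about 7), and the documents give no means or SDs.
- A reader might infer that rescoring one set of answers with item mean 6 and SD 1 turns a conservative test into an anti-conservative one. The matching sum has SD 5 and r = 1.10, still slightly conservative.
- A reader might infer that BP control power will drop to the low sixties. The simple formula ignores the person and practice effects, and the 29% rate comes from another trial. Here entry requires uncontrolled BP, so usual-care control may be far lower and the inflation correspondingly small.

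**Conclusion.** The point holds, with most of its weight on commitment and trust. There the model contradicts the outcome definitions in the same paragraph, and the standard errors are right only if the variance happens to equal the mean. The size of the error, and for sum scores its direction, depends on scoring and spread that the documents do not give. Under the assumed values it runs from a standard error about three times too large to one about a quarter too small.

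For BP control the fault is smaller and one-sided. The risk ratio can be estimated, but intervals are too wide by a factor of about 1.04 to 1.25, depending on the control rates and the model. Simulated power was 77% against 83%. There is no added false-positive risk for that outcome from this source.

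**What to change.** - **Commitment:** state whether items are averaged or summed, and replace the Poisson model with a linear mixed model.
- **Trust:** define the ordered categories and use a cumulative-logit mixed model.
- **BP control:** use a binomial GLMM and report a standardised risk difference and risk ratio. Alternatively, keep Poisson and specify cluster-robust standard errors with a small-sample correction, since there are only 10 practices.

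The cost is revised wording in sections 6.4.3.2 and 6.4.3.3 and a scoring line in 6.1.4. It needs no new data, and all of these models can be fitted in the software the plan already names (Stata, SAS and R). The change should be made before outcome data are analysed.

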Provider: The 12-item Physician Trust in the Patient Scale (PTPS) assesses the provider's perspective of patient behaviors that characterize high and low-trust relationships. The PTPS includes 2 subscales; the first asks about providers' expectations that patients will behave in ways that fulfill their roles in providing accurate and complete histories, asking questions, and adhering to treatment plans. The second subscale includes items about respecting the provider's time and personal boundaries. The PTPS has high internal reliability ($\alpha=0.93$), and convergent and discriminant validity. Prior research has found an association between low PTPS scores and patient non-adherence. To examine mutual trust, we will dichotomize scores on the TPS and PTPS into high and low trust values and compare the level of congruence between patients' and providers' score as: fully congruent, partially congruent, and incongruent. Like relationship commitment, we will apply text analysis to EHR-derived clinical notes and MyChart secure messages to assess *behavioral indicators* of trust. For example, we will examine patient self-disclosure of problematic behaviors where one could be judged poorly for engaging in that behavior (e.g., non-adherence to medications), and provider's response to the self-disclosure (e.g., use of non-judgmental language vs. admonishing the patient).

Moderator Variables

For the secondary aim 2, we will evaluate the potential moderating roles of practice- and individual-level factors on ALTA implementation at the practices. We will administer measures at baseline and 12 months (Table 2). All measures will be administered to clinical and nonclinical staff and administrative leadership at the practices. Based on our prior work, we expect a response rate of 70% across practices. Individuals will receive an incentive for timely completion of the surveys (n=204).

Practice-level measures

Organizational change process capability is a validated tool specifically applicable to primary care practice. The survey is divided into three domains that correspond to the three domains

of the Ingersoll definition of capacity to manage change: (1) history of change; (2) plans for continuous organizational refinement; and (3) ability to initiate and sustain change.

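### Patient-provider trust is called ordinal without saying which variable, how many levels or which cuts, and no analysis of the full Trust in Physician Scale score is planned

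*Combined protocol and SAP*

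**What the plan says.** Section 6.4.3.3 names two relationship outcomes, commitment first and trust second, and gives their analysis scale in one sentence: "Relationship commitment will be defined as a continuous variable while patient-provider trust will be categorized as ordinal". It gives no number of levels, no cut points and no reason for treating the two differently. The same section puts both outcomes under one model: "A Poisson regression model will be used specifying a fixed effect for time, a fixed effect for treatment, a time by treatment interaction".

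Section 6.1.4 describes two trust instruments, one for each side of the relationship. For the patient: "The 11-item Trust in Physician Scale (TPS) assesses a patient's interpersonal trust in their doctor", with 5-point responses. For the provider: "The 12-item Physician Trust in the Patient Scale (PTPS) assesses the provider's perspective of patient behaviors that characterize high and low-trust relationships".

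The only categorisation described is also in Section 6.1.4: "To examine mutual trust, we will dichotomize scores on the TPS and PTPS into high and low trust values". Congruence is then to be compared between "patients' and providers' score as: fully congruent, partially congruent, and incongruent". The cut between high and low is not stated. Table 2 lists mutual trust as the trust measure.

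No section specifies an analysis of the full TPS or PTPS score. The power statement in Section 6.4.2 concerns BP control only.

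**The concern.** The commitment scale has 5 items with 7-point responses; the TPS has 11 items with 5-point responses. The scale with more possible values is the one that appears to be coarsened, and the plan does not say how. Three things are at stake.

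- **Precision.** If the TPS is grouped, the comparison of the ALTA and usual-care phases loses power. Repairing the regression family would not restore it.
- **Pre-specification.** With no cut fixed in advance, the result can depend on a cut chosen later.
- **Change over time.** Section 4.4 asks whether changes in the relationship go with changes in adherence and BP control. Grouping hides any change that stays within a category.

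**Working it through.** The documents give no effect size, SD or power for trust, so there is no stated figure to reproduce. The check has two parts.

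**1. Which variable could be meant**

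If items are scored from 1 and summed (an assumption), commitment runs from 5 to 35, which is 31 values. The TPS runs from 11 to 55, which is 45 values. Section 6.4.3.3 allows three readings:

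- (a) a grouped TPS score;
- (b) the congruence classes of Section 6.1.4;
- (c) the TPS score with every value kept but modelled as ordinal.

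Reading (b) is not fully defined. Two high/low scores give four cells: high/high, low/low, high/low and low/high. The text does not say which of these is only partially congruent. Congruence also answers a different question from whether ALTA raises trust. A low/low pair is congruent, and if ALTA raises the patient to high the pair becomes high/low, so congruence falls while trust rises.

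Pairing is a further gap. Provider trust is collected in the staff survey (Sections 6.3.5 and 6.3.6). That survey is anonymous, and its baseline and 12-month rounds are not linked (Sections 6.3.2 and 6.3.6). No section shows how a provider's answers would be matched to a patient.

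**2. Information lost under reading (a)**

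Assumptions, none of them from the documents: a normal score, a small location shift, an analysis suited to ordered categories, clustering ignored, and the cuts shown. The relative efficiency of the grouped score against the full score is

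E = Σ over categories of [φ(lower cut) − φ(upper cut)]² / p,

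where φ is the standard normal density and p the share in each category. For two groups this reduces to φ(z)² / [p(1−p)].

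- Median split: 0.3989² / 0.25 = 0.637.
- 80/20 split: 0.2800² / 0.16 = 0.490.
- Tertiles: 2 × 0.3636² / (1/3) = 0.793 (the middle term is zero).
- Equal quartiles: 2 × [0.3178² + (0.3989 − 0.3178)²] / 0.25 = 0.861.
- Rank or proportional-odds model on all values, reading (c): 3/π = 0.955.

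For a comparison with 80% power on the full score (two-sided 0.05), power after grouping is Φ[(1.960 + 0.842)√E − 1.960].

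| Form of the outcome | E | Loss | Power |
|---|---|---|---|
| Full score, continuous | 1.00 | 0% | 80% |
| Ordinal model, all values | 0.955 | 4.5% | 78% |
| Equal quartiles | 0.861 | 13.9% | 74% |
| Tertiles | 0.793 | 20.7% | 70% |
| Median split | 0.637 | 36.3% | 61% |
| 80/20 split | 0.490 | 51.0% | 50% |

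Under these assumptions the median is the most efficient place for a two-way cut, so any high/low split loses at least 36%. The other rows are not bounds. Equal quintiles lose 10.3%, ten equal groups 4.1% and a 90/10 split 65.8%.

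**The case against.** The best reply is that Section 6.4.3.3 probably refers to congruence. Trust is measured from both sides, Table 2 lists mutual trust, and the congruence classes are the only multi-level trust variable in the documents. If that is the outcome, it is a different estimand. The grouped-score efficiencies do not apply to it, and a patient's TPS score cannot replace it. This stands as a limit on the arithmetic, but it does not remove the gap. The section does not name the variable, the middle class has no definition, no route to forming pairs is described, and congruence does not show whether ALTA raises trust.

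A second reply is that being categorised as ordinal may only describe the variable type, with every score value kept. The loss is then about 4.5% or less. That reading is possible, and the plan should say so if it is meant.

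A reader might also infer that the plan discards some 14% to 51% of the information for no benefit. The documents do not support this. The two ends correspond to equal quartiles and an 80/20 split, and neither appears in the plan. Section 6.1.4 also states a purpose for the categories, the study of mutual trust.

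Finally, trust is a tertiary outcome, ranked behind commitment, and the plan claims no power for it. This is correct and limits the weight of the point.

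**Conclusion.** The point holds as a gap in specification with a probable loss of precision. The ordinal trust outcome is not identified, its levels and cuts are not given, and the full TPS score is not analysed anywhere. The size depends on what is meant. For a grouped TPS it is about 14% at quartiles, 21% at tertiles and at least 36% for any high/low split; for an ordinal model on all values it is about 5% or less. These figures rest on a normal score, a small shift, assumed cuts and no clustering. They illustrate the cost and are not the plan's known loss. If congruence is the intended outcome they do not apply, and the problem is that the effect of ALTA on patient trust itself would go unestimated. The bearing on the trial's main conclusions is limited.

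**What to change.** In Section 6.4.3.3:

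1. Make the total TPS score the patient-trust outcome for the comparison of the ALTA and usual-care phases. Analyse it as continuous in a linear (Gaussian) mixed model, or with an ordinal model on all score values. The model has to be written out: the section specifies Poisson regression for both outcomes, so there is no linear model for commitment to copy.
2. Keep mutual-trust congruence as a separate, secondary analysis. State the high/low cut points and define all three classes in advance. Run it only if patient-provider pairs can be formed, and say how.
3. Analyse the PTPS on its full score as repeated cross-sections by practice and phase. A longitudinal model with a person effect cannot be fitted, because the staff surveys are anonymous and unlinked. Confirm that the survey records the practice.

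The cost is SAP wording and a small amount of extra analysis. The TPS analysis needs no new data. The congruence analysis may not be feasible as the data are now collected.
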